13.5 Vital Signs

Vital signs (systolic and diastolic blood pressure [SBP and DBP], pulse rate, and body temperature) will be summarized using descriptive statistics at baseline and at each post-baseline time point. Changes from baseline will also be summarized.

Blood pressure will be classified as normal or elevated based on reference ranges as per Table below. Subjects with markedly abnormal changes will be listed and tabulated separately.

Age		Absolute Values		Change (Absolute) from Baseline	
		Normal	Elevated	Abnormal Change	Markedly Abnormal Change
2-6 yrs old	SBP	<105 mm Hg	≥105 mm Hg	≥20 mm Hg	≥30 mm Hg
	DBP	<67 mm Hg	≥67 mm Hg	≥10 mm Hg	≥20 mm Hg
7-11 yrs old	SBP	<110 mm Hg	≥110 mm Hg	≥20 mm Hg	≥30 mm Hg
	DBP	<74 mm Hg	≥74 mm Hg	≥10 mm Hg	≥20 mm Hg
12-17 yrs old	SBP	<120 mm Hg	≥120 mm Hg	≥20 mm Hg	≥30 mm Hg
	DBP	<80 mm Hg	≥80 mm Hg	≥10 mm Hg	≥20 mm Hg

Pulse will be classified as low, normal, or high based on reference ranges as per Table below. Subjects with abnormal (low or high) values will be listed and tabulated separately.

	Absolute Values		
	Low	Normal	High
2-10 yrs old	<60 bpm	60-140 bpm	>140 bpm
11-17 yrs old	<50 bpm	50-100 bpm	>100 bpm

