
 Incidence, frequency, and duration of treatment emergent adverse events (TEAEs) and serious adverse events (SAEs) Change from Baseline in laboratory values Change from baseline in vital signs Mean Investigator-assessed LTS scores by visit (overall and sensitive areas) Tapinarof plasma PK parameters on Day 1, if data permit, including: 
 area under the plasma concentration versus time curve from time zero to the last quantifiable concentration (AUC_{0-last}) maximum plasma concentration (C_{max}) time to maximum plasma concentration (t_{max}) time of last quantifiable concentration (t_{last}) Tapinarof plasma concentration on Day 28 	
Secondary:	

 Change in vIGA-AD™ score from Baseline at each study visit Proportion of subjects who have a vIGA-AD™ score of clear or almost clear (0 or 1) at each study visit Proportion of subjects with \geq50% improvement in EASI score from Baseline at each study visit Proportion of subjects with \geq75% improvement in EASI score from Baseline at each study visit Proportion of subjects with \geq90% improvement in EASI score from Baseline at each study visit Mean change and percent change in EASI score from Baseline at each study visit Mean change and percent change in %BSA affected from Baseline at each study visit Mean change and percent change in BSA x vIGA-AD™ values from Baseline at each study visit Proportion of subjects with a Baseline PP-NRS score \geq 4 who achieve \geq 4-point reduction in the PP NRS from Baseline at each study visit Proportion of subjects \geq 12 years old with a Baseline PP-NRS score \geq 4 who achieve a \geq 4-point reduction in PP-NRS score from Baseline at each study visit Proportion of subjects 2 to $<$ 12 years old with a Baseline PP-NRS score \geq 4 who achieve a \geq 4-point reduction in PP-NRS score from Baseline at each study visit Mean change in PP-NRS score from Baseline to Day 28 at each study visit by age group 	
Statistical Methods:	
Safety Analyses:	

 Analyses of the safety endpoints will be based upon the Safety population, which is defined as all enrolled subjects who receive at least 1 application of study drug. 	

- AEs will be summarized as incidence rates of any AEs, TEAEs, AEs of special interest, treatment-related TEAEs, TEAEs leading to study drug discontinuation, TEAEs leading to study discontinuation, and SAEs.

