- Changes in laboratory parameters and vital signs will be summarized using shift tables and descriptively for quantitative measures by visit.
- LTS scores will be summarized by visit.

Pharmacokinetics:

- Plasma concentration data will be listed and summarized by study visit. PK parameters will be presented in tabular and/or graphical format and summarized descriptively if data permit

Efficacy Analyses:

- Analyses of efficacy endpoints will be based upon the Safety population. Proportions will be summarized using frequency counts and percentages, and mean changes and percent changes will be summarized using descriptive statistics (mean, median, standard deviation, minimum and maximum).

Schedule of Assessments

Table 1: Schedule of Assessments

Procedures and Assessment	Screening	Treatment Phase					FU ^a	ET ^b
	V1	V2	V3	P/C	V4	V5	NA	
	Day -30 to Day -1	Baseline, Day 1	Day 8 (±1 day)	Day 15 (±2 days)	Day 28 (±2 days)	Day 35 (±3 days)	NA	
Informed consent	X							
Inclusion and exclusion criteria	X	X						
Demography	X							
Fitzpatrick skin type	X							
Brief physical exam ^c	X	X	X			X	X	X
Medical history ^d	X	X ^e						
Pregnancy test (females of child-bearing potential) ^f	X	X ^g				X		X
Blood sample for clinical laboratory assessments ^h	X					X	X ⁱ	X
Urinalysis	X					X	X ⁱ	X
Vital signs ^j	X	X	X			X	X	X
Study drug Dispensation / Collection ^k		D	C/D			C		C
Review instructions for study drug application ^l		X	X	X				
Dispense/collect subject diary of study drug application		D	C/D			C		C
Tapinarof cream administration in-clinic under site supervision ^m		X	X					
PK samples ⁿ	X	X				X		
AE/SAE review	X	X	X	X	X	X	X	X
Concomitant medication review	X	X	X	X	X	X	X	X
vIGA-AD TM score ^o	X	X	X			X	X	X
%BSA affected ^p	X	X	X			X	X	X
EASI ^p		X	X			X	X	X
LTS assessment by Investigator ^q		X	X			X		
PP-NRS (assessed pre-dose at visit, as applicable) ^r		X	X			X		
Enrollment (optional) in open-label long-term safety study						X		

- a. The Follow-up Visit will be performed for any subject who fails to qualify for participation in the open-label long-term safety study or qualifies to participate in the open-label long-term safety study but elects not to enroll in that study. A follow-up visit will be not completed for a subject who terminates early.
- b. Subjects who withdraw from the study before Day 28 (Visit 4) will complete an Early Termination Visit.

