10.4.2 Safety Analyses

The Safety Population will be used in the analysis of safety data. Data will be listed by subject. No formal statistical comparisons will be made for safety data.

The number and proportion of subjects with TEAEs will be summarized by system organ class, and preferred term for all TEAEs, all TEAEs considered by the Investigator to be related to study drug, all SAEs, and all TEAEs leading to study drug discontinuation.

Laboratory values will be classified as normal, low or high based on normal ranges supplied by the laboratory. Changes from baseline in abnormality status will be summarized using shift tables. For quantitative laboratory measures, observed values and changes from baseline will be summarized descriptively.

Observed vital sign values (systolic and diastolic blood pressure, pulse rate, and body temperature) and change from baseline in vital signs will be summarized similarly to the laboratory values.

LTS scores will be summarized by visit.

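### SAP 13.5 has no low category for blood pressure and does not separate falls from rises, so the categorical output counts any low reading as normal

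*SAP*

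**What the plan says.** The protocol synopsis lists "Change from baseline in vital signs" among the primary endpoints. On method, the synopsis says: "Changes in laboratory parameters and vital signs will be summarized using shift tables and descriptively for quantitative measures by visit". Protocol 10.4.2 first sets the laboratory method: "Laboratory values will be classified as normal, low or high based on normal ranges supplied by the laboratory", with shift tables for abnormality status and descriptive summaries for quantitative measures. It then says of vital signs, naming systolic and diastolic pressure, pulse and temperature, that observed values and "change from baseline in vital signs will be summarized similarly to the laboratory values".

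SAP 13.5 plans descriptive statistics for observed vital signs and for changes from baseline. For blood pressure it adds: "Blood pressure will be classified as normal or elevated based on reference ranges as per Table below". Its table gives each age band a normal and an elevated range, and two change columns (abnormal and markedly abnormal) under the heading "Change (Absolute) from Baseline". The only separate output it promises for the change columns is: "Subjects with markedly abnormal changes will be listed and tabulated separately". In the same section, by contrast, "Pulse will be classified as low, normal, or high based on reference ranges as per Table below". SAP 14 states that nothing departs from the protocol's analyses.

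**The concern.** A two-level scale with an open lower end cannot show low blood pressure. Readings that are low for a child's age are counted with ordinary ones under a label that says they are normal. The change columns could have covered this gap, but they state no direction and only the more extreme column leads to a separate output. The endpoint is a primary safety endpoint in children aged 2 to 17, in a maximal-use study meant to look for systemic effects. A reader who relies on the categorical table could conclude that there were no abnormal low values when the table was never able to display them.

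**Working it through.** No sample-size or power figure is involved. The check applies the SAP 13.5 cut-offs to low values and compares the result with the protocol.

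**1. Absolute categories.** All limits are from the SAP 13.5 table.

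| Age | Parameter | Normal | Elevated | Lower limit of normal |
|---|---|---|---|---|
| 2-6 | SBP | <105 | ≥105 | none |
| 2-6 | DBP | <67 | ≥67 | none |
| 7-11 | SBP | <110 | ≥110 | none |
| 7-11 | DBP | <74 | ≥74 | none |
| 12-17 | SBP | <120 | ≥120 | none |
| 12-17 | DBP | <80 | ≥80 | none |

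Three age bands × two parameters = six rows, none with a lower limit. The sentence above the table also names two categories, so this is not a column lost in text extraction.

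**2. Change columns.** In every age band the cut-offs are ≥20 mm Hg (abnormal) and ≥30 mm Hg (markedly abnormal) for SBP, and ≥10 and ≥20 mm Hg for DBP. The heading allows two readings:

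- As a magnitude, a fall and a rise of equal size get the same flag and are pooled.
- As a signed increase in mm Hg (absolute as opposed to percent), no fall of any size is flagged.

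**3. Worked example, age 2-6, SBP 95 to 70 mm Hg (illustrative values).**

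- Baseline: 95 < 105, so normal.
- Post-baseline: 70 < 105, so normal.
- Change: 70 − 95 = −25, magnitude 25.
- As a magnitude: 25 ≥ 20, so abnormal change; 25 < 30, so not markedly abnormal.
- As a signed increase: −25 is below both cut-offs, so no flag.
- On either reading, SBP does not bring this child into the separate listing and table.

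For readings in whole mm Hg, the largest falls that stay outside the separate output on the magnitude reading are 30 − 1 = 29 for SBP and 20 − 1 = 19 for DBP. A 14-year-old going from 95 to 66 (a fall of 29) is normal at both visits (95 and 66 are both below 120) and is not separately listed for SBP.

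**4. Comparison with the protocol.**

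- Laboratory values, protocol 10.4.2 and SAP 13.4: normal, low or high, with shift tables.
- Pulse, SAP 13.5: low, normal or high, with low and high values listed and tabulated separately.
- Blood pressure, SAP 13.5: normal or elevated only.
- Vital-sign shift tables: promised in the synopsis; none planned in SAP 13.5; no change declared in SAP 14.

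**The case against.** The strongest reply is that little is lost. Protocol 10.1 and SAP section 6 put all safety data in by-subject listings. The endpoint is change from baseline, and SAP 13.5 summarises it descriptively. With minimum and maximum shown by age group, and about 12 subjects per cohort, a low minimum or a mean fall would be visible. A reading that the investigator judges clinically significant is also an adverse event under protocol 8.1.1. All of this stands, and it limits the point to the categorical outputs. A reader might infer that low readings go unlisted or that the primary endpoint is not analysed; the documents support neither.

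The second reply is that the protocol never states a low/normal/high method for vital signs. It applies those classes to laboratory values, using ranges that a laboratory supplies, and links vital signs only by the word similarly. That word could refer to the descriptive summaries alone, and protocol 10.4 leaves detail to the SAP. This also stands in part. A reader might infer a flat contradiction on the three classes, but the text supports only a poor fit. The synopsis promise of vital-sign shift tables is explicit, although a normal/elevated shift table would satisfy it. The absence of any such table is therefore the clearer mismatch.

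A reader might also fault the pulse bands (2-10 and 11-17) for cutting across the 7-11 cohort. That is not a defect. Each child is judged against the limits for their own age, and any age-banded limit has a step somewhere.

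**Conclusion.** The point holds for the categorical blood-pressure outputs. All six rows lack a lower limit, so any low reading is counted as normal, and the change flags either pool falls with rises or miss falls altogether. The size of the gap follows from the stated cut-offs: on the magnitude reading, whole-number falls of up to 29 mm Hg SBP or 19 mm Hg DBP never reach the separate output; on the signed reading, no fall does. The conclusion rests on the table as printed and on SAP 13.5 being the full plan for vital signs. It does not depend on any assumed clinical limit, and nothing in the documents suggests that a low-pressure signal is expected. The missing shift tables are an undeclared departure from the synopsis. This should be corrected, but it does not threaten the study's primary conclusions, because the underlying values are still summarised and listed.

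**What to change.** Amend SAP 13.5 and, if needed, SAP 14 before database lock. SAP section 6 treats analyses added after lock as post hoc.

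1. Add a low category for SBP and DBP in each age band, with limits set by the sponsor. The documents give none, and none is proposed here.
2. State what the change heading means, and tabulate increases and decreases separately at the existing cut-offs (20 and 30 mm Hg for SBP, 10 and 20 mm Hg for DBP).
3. Add the vital-sign shift tables promised in the synopsis, or record their omission in SAP 14. SAP 13.5 defines no categories for body temperature, so a shift table for it would need limits as well.

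The cost is six lower limits to specify (three age bands × two parameters), slightly larger tables to program, and either the shift tables or one entry in SAP 14. All the blood-pressure data are already collected.

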13.6 Physical Examination

Physical examination results will be included in data listings only.

14. CHANGES TO PROTOCOL-SPECIFIED ANALYSES

Not applicable. There are no changes to the protocol-specific analyses.

Dermavant Sciences, Inc.
DMVT-505-2104

Statistical Analysis Plan, v1.0
08SEP2022

15. REFERENCES

16. APPENDICES

APPENDIX A: PRESENTATION OF DATA AND PROGRAMMING SPECIFICATIONS

General

- Specialized text styles, such as bold, italics, borders, shading, and superscripted and subscripted text will not be used in tables, figures, and data listings unless they add significant value to the table, figure, or data listing.
- Only standard keyboard characters are to be used in tables and data listings.
- Special characters, such as nonprintable control characters, printer-specific, or font-specific characters, will not be used on a table, figure, or data listing.
- Hexadecimal character representations are allowed (eg, μ , α , β).
- All footnotes will be left justified and at the bottom of a page. Footnotes must be used sparingly and must add value to the table, figure, or data listing.
- Throughout the data cleaning process, all attempts will be made to avoid missing values for TEAE relationship and severity. If either or both are missing, no imputation will be performed.

Tables

- Means and medians will be presented to 1 more decimal place than the raw data. Standard deviations will be presented to 2 more decimal places than the raw data. Minimums and maximums will be reported with the same number of decimal places as the raw data. If raw data has more than 2 decimal places, the same rule will be applied as the raw data with 2 decimal places.
- Percentages will be presented to the tenths place.
- For frequency counts of categorical variables, categories whose counts are zero will be displayed for the sake of completeness. For example, if none of the subjects discontinue due to “lost to follow-up,” this reason will be included in the table with a count of 0. Categories with zero counts will have zero percentages displayed. Results of one hundred percentages and zero percentages will have the same representation in tables as other percentages.
- Lower and upper CI values must be presented to 1 decimal place more than the raw/derived data (ie, to the same number of decimal places as the mean).
- Percentiles (eg, 25%, 75%) must be presented to 1 decimal place more than the raw/derived data.
- The last footnotes will be
 - “Source: xxx”, where xxx indicates the source **table number(s)** if applicable (in case aggregated results like mean or median are plotted), or the source listing(s) (in case individual responses are plotted), and/or source dataset(s) (eg, ADaM).
 - “PROGRAM SOURCE: ...\\xx.sas, DDMMYY hh:mm”.

Figures

- Legends will be used for all figures with more than 1 variable or item displayed. Subject count (n=xx) will be included, as appropriate.
- Figures will be in black and white but can be in color to add value to the clarity and readability of a figure. Lines must be wide enough to see the line after being copied.
- The last footnotes will be
 - “Source: xxx”, where xxx indicates the source listing number(s) and/or source dataset(s) (eg, ADaM).
 - “PROGRAM SOURCE: ...\\xx.sas DDMMMYY hh:mm”.

Listings

- If not otherwise specified, all data listings will be sorted by subject number, visit, and date/time, as appropriate.
- All date values will be presented in a SAS date (eg, 29AUG2001) format.
- All observed time values will be presented using a 24-hour clock HH:MM:SS format (eg, 01:35:45 or 11:26). Seconds will only be reported if they were measured as part of the study.
- The last footnote will be
 - “PROGRAM SOURCE: ...\\xx.sas DDMMMYY hh:mm”.

Standard Calculations

Variables requiring calculation will be derived using the following formulas:

- **Days** – A duration expressed in days between 1 date (date1) and another later date (date2) is calculated using the formulas noted below:
duration in days = date2 – date1 + 1
- **Months** – A duration expressed in months is calculated using the INTCK function of SAS as follows: months=intck('month','date1'd,date2'd, 'continuous').
- **Years** – A duration expressed in years between one date (date1) and another later date (date2) is calculated as follows:
duration in years = intck('year', 'date1'd, 'date2'd, 'continuous').
- **Age** – will be reported in EDC based on informed consent date
- **Height** – Height entries made in inches (in) are converted to centimeters (cm) using the following formula:
height (cm) = height (in) × 2.54.
- **Weight** – Weight entries made in pounds (lb) are converted to kilograms (kg) using the following formula:
weight (kg) = weight (lb)/2.2046.
- **Temperature** – Temperature entries in degrees Fahrenheit are converted to degrees centigrade using the following formula:
temp (degrees centigrade) = 5/9 × [temp (degrees Fahrenheit) – 32].

- **Body Mass Index (BMI)** – BMI is calculated using height (cm) and weight (kg) using the following formula:
$$\text{BMI (kg/m}^2\text{)} = \text{weight (kg)}/[\text{height (cm)}/100]^2\text{].}$$
- **Change from baseline** – Change from baseline will be calculated as:
$$\text{Change} = \text{post-baseline value} - \text{baseline value}.$$
- **Percent change from baseline** – Percent change from baseline will be calculated as:
$$\text{Percent change from baseline} = (\text{post-baseline value} - \text{baseline value})/\text{baseline value} \times 100.$$

APPENDIX B: SAS PROGRAMMING QC REQUIREMENTS

Derived datasets are independently reprogrammed by a second programmer. The separate datasets produced by the 2 programmers must match 100%. Detailed specifications for the derived datasets are documented in the study Analysis Dataset (ADaM) Specifications provided to Dermavant at study conclusion.

Tables are independently reprogrammed by a second programmer for numeric results.

Listings are checked for consistency against corresponding tables, figures, and derived datasets.

Figures are checked for consistency against corresponding tables and listings, or independently reprogrammed if there are no corresponding tables or listings.

The entire set of TLFs is checked for completeness and consistency prior to its delivery to Dermavant by the lead biostatistician and a senior level, or above, reviewer.
